6.3.2. PRO endpoints

All PRO analyses will be performed for PD-L1 positive patients and for patients unselected for PD-L1 expression and will be based on the FAS.

6.3.2.1. PRO instruments

Patient-reported outcomes of HRQoL will be evaluated using FACT-Kidney Symptom Index (FKSI-19) and EQ-5D-5L. A 9-item subscale of the FKSI-19 known as the FKSI-Disease Related Symptoms subscale (FKSI-DRS) measures advanced kidney cancer disease related symptoms.

The primary PRO endpoint will be the time to symptom deterioration (TTD) which is defined as the time from date of randomization to the first time the patient's score shows a 3-point or greater decrease in FKSI-DRS.

6.3.2.2. Scoring procedure

The FKSI-19 and EQ-5D-5L will be scored according to their respective validation papers and user's guides. For the EQ-5D-5L, utility scores will be collated using the published weights (tariffs) for the United Kingdom (UK). Missing values in the instruments will also be handled following the guidance from their respective User Manuals.

6.3.2.3. Instrument completion rates

For each treatment arm and at each time point, the number and percentage of patients who complete the FKSI-19, FKSI-DRS and EQ-5D-5L will be summarized, as will the reasons for non-completion of these measures. An instrument is considered complete if at least one item was answered by the patient.

6.3.2.4. Descriptive summaries over time

Separate tables will be used to summarize, for each treatment arm, the mean (and SD), and median (and range) of absolute scores and change from baseline of the FKSI-19, FKSI-DRS EQ-5D-5L, and EQ-5D-5LVAS at each time point. A line chart depicting the means along with standard error (SE) error bars over time will be provided for each scale in each treatment arm.

6.3.2.5. Time-to-event endpoints

Time to deterioration (TTD) endpoint

A 3-point change from baseline in FKSI-DRS has been established as clinically meaningful.

Time to deterioration (TTD) is defined as the time from the date of randomization to the first time the patient's score shows a 3-point or greater decrease from baseline in FKSI-DRS.

TTD data will be censored at the last time when a patient completed the assessment for patients who have not deteriorated.

The treatment effect on TTD will be estimated using a Cox's Proportional Hazard model stratified by the randomization strata to calculate the hazard ratio for the experimental arm vs control arm.

Each stratum will define a separate baseline hazard function (using the 'STRATA' statement in SAS PROC PHREG), i.e. for the i -th stratum the hazard function is expressed as: $h(i;t) = h(i,0;t) \exp(x\beta)$, where $h(i,0;t)$ defines the baseline hazard function for the i -th stratum and x defines the treatment arm (0=control arm, 1= experimental arm) and β is the unknown regression parameter.

Ties will be handled by replacing the proportional hazards model by the discrete logistic model (Ties=Discrete option in SAS PROC PHREG).

Kaplan-Meier estimates (product-limit estimates) will be presented by treatment arm together with a summary of associated statistics including the median TTD time with 2-sided 95% CIs. The CIs for the median TTD will be calculated according to Brookmeyer and Crowley (1982).

Time to Improvement (TTI) endpoint

A 3-point change from baseline in FKSI-DRS has been established as clinically meaningful.

Time to improvement (TTI) is defined as the time from the date of randomization to the first time the patient's score shows a 3-point or greater increase from baseline in FKSI-DRS.

TTI data will be censored at the last time when a patient completed the assessment for patients who have not improved.

TTI will be analyzed using the same methodology as TTD.

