The sample size for this study is determined based on the following:

1. the median PFS for patients receiving sunitinib is 11 months (Sutent Summary of Product Characteristics) and the median PFS for patients receiving avelumab in combination with axitinib is 16.9 months for PD-L1 positive patients and 15.7 months for patients unselected for PD-L1 expression; this, corresponds to a hazard ratio (HR) of 0.65 and 0.7, respectively under the exponential model assumption;
2. the median OS for patients receiving sunitinib is 26.4 months (Sutent Summary of Product Characteristics) and the median OS for patients receiving avelumab in combination with axitinib is 37.7 months for PDL1 positive patients and 35.2 months for patients unselected for PD-L1 expression; this corresponds to a HR of 0.7 and 0.75, respectively under the exponential model assumption;

3. PFS drop-out rate of approximately 15% and OS drop-out rate of approximately 5%;
4. 70% of the randomized patients are PD-L1 positive;
5. non-uniform patient accrual accomplished over a 21 month period.

The sample size of approximately 830 patients will also allow an assessment of PFS and OS in patients unselected for PD-L1 expression.

If H_{01} is rejected then PFS in patients unselected for PD-L1 expression can be tested and 490 PFS events by BICR assessment will be required to have at least 90% power to detect a HR of 0.70 using a 1-sided log rank test at a significance level of 0.004, and a 2-look group sequential design with Lan-DeMets (O'Brien-Fleming) α -spending function to determine the efficacy boundary.

If either H_{02} or H_{03} are rejected, then OS in patients unselected for PD-L1 expression can be tested at the sum of the significance levels associated with the significant H_{02} and H_{03} tests (see Figure 1). With 534 OS events, the power is 91% (if both H_{02} and H_{03} are rejected), 90% (if H_{02} is rejected and H_{03} is not rejected) or 74% (if H_{02} is not rejected and H_{03} is rejected) to detect a HR of 0.75 using a 1-sided log rank test at a significance level of 0.025, 0.021 or 0.004, respectively, and a 4-look group sequential design with Lan-DeMets (O'Brien-Fleming) α -spending function to determine the efficacy boundary.

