Kaplan-Meier estimates (product-limit estimates) will be presented by treatment arm together with a summary of associated statistics including the median PFS time with 2-sided 95% CIs. In particular, the PFS rate at 6, 12, 18, 24, 30, 36 months will be estimated with corresponding 2-sided 95% CIs. The CIs for the median will be calculated according to Brookmeyer and Crowley and the CIs for the survival function estimates at the time points defined above will be derived using the log-log transformation according to Kalbfleisch and Prentice (conftype=loglog default option in SAS Proc LIFETEST) with back transformation to a CI on the untransformed scale. The estimate of the standard error will be computed using Greenwood's formula.

Frequency (number and percentage) of patients with each event type (PD or death) and censoring reasons will be presented by treatment arm. Reasons for censoring will be summarized according to the categories in Table 10 following the hierarchy shown:

Table 10. PFS Censoring Reasons and Hierarchy

Hierarchy	Condition	Censoring Reason
1	No adequate baseline assessment	No adequate baseline assessment
2	Start of new anti-cancer therapy.	Start of new anti-cancer therapy
3	Event after 2 or more missing or inadequate post-baseline tumor assessments/date of randomization	Event after 2 or more missing assessments ^a
4	No event and [withdrawal of consent date \geq date of randomization OR End of study (EOS) = Subject refused further follow-up]	Withdrawal of consent
5	No event and lost to follow-up in any disposition page	Lost to follow-up
6	No event and [EOS present OR disposition page for any epoch after screening says patient will not continue into any subsequent phase of the study] and no adequate post-baseline tumor assessment	No adequate post-baseline tumor assessment
7	No event and none of the conditions in the prior hierarchy are met	Ongoing without an event

^a 2 or more missing or inadequate post-baseline tumor assessments.

The PFS time or censoring time and the reasons for censoring will also be presented in a patient listing.

Time of Follow-Up for PFS

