6.3.2.6. Binary endpoints

The proportion of patients who have improved from baseline at Cycle 5, defined as a 3-point or greater increase from baseline in FKSI-DRS, will be summarized using descriptive statistics as described in Section 5.2.3. Chi-square test will be used to compare the proportions between the experimental arm and control arm. Patients who did not complete the first 5 cycles of treatment and did not show improvement prior to EOT will be counted as not having improved.

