6.3.2.8. Sensitivity Analyses

Sensitivity analyses based on a 2-point, 4-point and 5-point decrease from baseline in FKSI-DRS will be conducted for TTD; similarly, sensitivity analyses based on a 2-point, 4-point and 5-point increase from baseline in FKSI-DRS will be conducted for TTI. Cumulative distribution function plots of the change from baseline in the FKSI-DRS for Cycle 2, 4, 6, 8 and 10 will also be presented.

For TTD and TTI, the primary analyses will include data from baseline up to EOT assessment (not including EOT). Sensitivity analyses for these endpoints will include all assessments from baseline to the end of the safety follow-up period.

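### Time to improvement in FKSI-DRS censors patients who die or stop treatment without improving, so one minus Kaplan-Meier overstates the proportion who improve, by an amount that depends on inputs the plan does not give

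*SAP*

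**What the plan says.** SAP 6.3.2.5 defines TTI as the time from randomization to the first gain of at least 3 points over baseline in FKSI-DRS. The only censoring rule is that "TTI data will be censored at the last time when a patient completed the assessment for patients who have not improved". Death and stopping treatment have no rule of their own.

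The method is carried over from time to deterioration (TTD): "TTI will be analyzed using the same methodology as TTD". That means a stratified Cox model, and for display, "Kaplan-Meier estimates (product-limit estimates) will be presented by treatment arm together with a summary of associated statistics including the median TTD time".

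The window is set in SAP 6.3.2.8: "For TTD and TTI, the primary analyses will include data from baseline up to EOT assessment (not including EOT"). The same section adds a wider analysis: "Sensitivity analyses for these endpoints will include all assessments from baseline to the end of the safety follow-up period".

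SAP 6.3.2.6 has a separate binary endpoint, improvement at Cycle 5. There, patients who did not complete five cycles and "did not show improvement prior to EOT will be counted as not having improved".

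The text available plans no cumulative incidence analysis for any of these endpoints.

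**The concern.** With the window closed at EOT, a patient who dies or stops treatment unimproved has no further chance of a counted improvement. Kaplan-Meier censoring assumes that such a patient stays at risk and would go on to improve at the same rate as those still on treatment. The curve then describes a setting in which nobody dies or stops. The SAP does not say that this is the quantity wanted, and a reader will take the curve and its median as the proportion who improved and when.

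Three consequences follow.

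- The proportion read off the curve is too high.
- The excess depends on how long patients stay on treatment. The plan expects longer PFS on the combination, so two arms with the same Kaplan-Meier curve could have different proportions improving on treatment.
- Adjacent sections of the SAP treat the same patients in opposite ways: censored for TTI, counted as not improved for the Cycle 5 endpoint. The two results cannot be reconciled with each other.

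**Working it through.** **Inputs.** SAP 5.1.1 gives median PFS of 11 months for sunitinib, and for the combination 16.9 months (PD-L1 positive) or 15.7 months (unselected). Median OS is 26.4 months for sunitinib and 37.7 or 35.2 months for the combination. The plan assumes exponential distributions. It gives no improvement rate and no time-on-treatment distribution. I therefore assume a median TTI of 9 to 36 months and use PFS as a proxy for time to stopping.

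**Step 1: the plan's own figures.** There is none for TTI. The medians do return the plan's hazard ratios: 11/16.9 = 0.651 and 11/15.7 = 0.701, against 0.65 and 0.70 stated. The stopping hazards are c = ln2/11 = 0.0630, ln2/15.7 = 0.0441 and ln2/16.9 = 0.0410 per month. Under the proxy, 78.0%, 65.3% and 62.6% have stopped by 24 months.

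**Step 2: formulas.** With constant, independent hazards h (improvement) and c (stopping):

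- one minus Kaplan-Meier = 1 − exp(−h·t)
- cumulative incidence = h/(h+c) × [1 − exp(−(h+c)·t)]

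**Step 3: one case in full.** Take a median TTI of 24 months, so h = ln2/24 = 0.0289. At 24 months one minus Kaplan-Meier is 50.0% in either arm. For sunitinib the cumulative incidence is 0.0289/0.0919 × [1 − exp(−0.0919 × 24)] = 0.314 × 0.890 = 28.0%. The excess is 22.0 points.

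**Step 4: the range.** Gaps are in percentage points, from unrounded values.

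| Stopping median (months) | Assumed median TTI (months) | 1 − KM at 24 m | Cumulative incidence at 24 m | Gap at 24 m | Gap at 12 m |
|---|---|---|---|---|---|
| 11 (sunitinib) | 9 | 84.3% | 53.1% | 31.2 | 15.6 |
| 11 | 24 | 50.0% | 28.0% | 22.0 | 8.3 |
| 11 | 36 | 37.0% | 20.2% | 16.8 | 5.9 |
| 15.7 (combination, unselected) | 9 | 84.3% | 60.1% | 24.2 | 11.6 |
| 15.7 | 24 | 50.0% | 32.7% | 17.3 | 6.2 |
| 15.7 | 36 | 37.0% | 23.7% | 13.3 | 4.5 |
| 16.9 (combination, PD-L1 positive) | 9 | 84.3% | 61.4% | 22.8 | 10.9 |
| 16.9 | 24 | 50.0% | 33.6% | 16.4 | 5.8 |
| 16.9 | 36 | 37.0% | 24.4% | 12.6 | 4.2 |

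At the same Kaplan-Meier share of 50%, the gap is 4.7 points larger on sunitinib than at 15.7 months (22.0 − 17.3) and 5.6 points larger than at 16.9 months (22.0 − 16.4).

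**Step 5: other inputs, still over 24 months.**

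- Rare improvement: a Kaplan-Meier share of 10% gives a gap of 3.6 to 4.8 points; 20% gives 7.0 to 9.4.
- Early improvement, with 30% to 70% of patients able to improve: a median of 1.5 months among them gives 2.4 to 8.4 points. Allowing medians up to 6 months widens this to 2.4 to 21.0.
- Death as the only competing event (OS medians, Kaplan-Meier shares of 10% to 95%): 1.9 to 15.9 points.

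**Step 6: the median.** Under constant hazards the share who ever improve is h/(h+c). This is below one half whenever h < c, that is, whenever the Kaplan-Meier median TTI exceeds the median time to stopping. With a median TTI of 24 months, the curve shows a median although only 31.4% of sunitinib patients ever improve on treatment (41.3% with a stopping median of 16.9 months, 39.5% with 15.7).

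**The case against.** Several objections have force.

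**Size.** A reader might infer that the plan itself builds in an overstatement of 13 to 31 points. It does not. The improvement rate is assumed, and the 24-month time point is a reviewer's choice: for PFS the SAP states that "the PFS rate at 6, 12, 18, 24, 30, 36 months will be estimated", but it names no such rates for TTI. The top value, 31, is reached only in the sunitinib arm.

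**Proxy.** PFS is a weak stand-in for time on treatment. Protocol 5.4.4 allows treatment past progression, and Protocol 3.1.1 lets combination patients continue on one drug alone. Both lengthen time on treatment, while toxicity stops shorten it.

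**Estimand.** Death rules out later improvement, but stopping treatment does not. Protocol 7.2.1 collects the questionnaire at EOT and afterwards with tumor assessments, and SAP 6.3.2.8 has an analysis that uses later data. Counting discontinuation as competing is therefore partly a choice of question. It is the right choice for the pre-EOT analysis, because that window makes later improvement uncountable. The wider analysis does not remove the problem, since death is still censored there.

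**Comparison between arms.** A reader might also infer that the treatment comparison is biased. The stratified Cox hazard ratio remains interpretable as a cause-specific ratio and is not inflated by this mechanism. The arm difference in the table arises with identical improvement hazards, so it reflects assumed time on treatment, not a hidden effect on symptoms.

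**Importance.** TTI carries no allocated alpha, and SAP 6.3.2.1 makes TTD the primary PRO endpoint. The Cycle 5 proportion already gives one unaffected summary of improvement, at a single visit. All of this stands, and it limits the weight of the point without removing it.

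**Conclusion.** The point holds in direction and is conditional in size. Once improvements count only before EOT, death and stopping treatment are competing events, and censoring them makes one minus Kaplan-Meier an upper bound on the proportion who improve. That follows from the stated method and needs no assumed rate. The conflict with the Cycle 5 rule is also plain from the text.

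The size rests on constant independent hazards, PFS as the stopping time and an assumed median TTI. Under the stated range it is material: 16.8 to 31.2 points for sunitinib and 12.6 to 24.2 for the combination at 24 months, and 5.9 to 15.6 and 4.2 to 11.6 at 12 months. Other plausible inputs bring it down to about 2 points. It should be quoted only with those assumptions attached.

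The change is worth making because the median is a named output and PROs are a listed secondary endpoint (Protocol 2.2). The primary PFS and OS analyses and their error control are not affected.

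**What to change.** In SAP 6.3.2.5, report TTI by arm as an Aalen-Johansen cumulative incidence with 95% confidence intervals.

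- For the pre-EOT analysis, take death and treatment discontinuation before improvement as competing events.
- For the sensitivity analysis to the end of safety follow-up, take death alone as competing. State that patients reaching the end of that window are censored.
- Describe the proportion and timing of improvement from these estimates, not from one minus Kaplan-Meier or the Kaplan-Meier median. Label any Kaplan-Meier curve that is kept as hypothetical, with no death or discontinuation.
- Keep the stratified Cox model, labelled as a cause-specific hazard ratio.

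The cost is a wording change and a little extra analysis on data already collected. The improvement percentages from the time-to-event display will be less favourable. The Cycle 5 proportion does not change.

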6.3.2.6. Binary endpoints

The proportion of patients who have improved from baseline at Cycle 5, defined as a 3-point or greater increase from baseline in FKSI-DRS, will be summarized using descriptive statistics as described in Section 5.2.3. Chi-square test will be used to compare the proportions between the experimental arm and control arm. Patients who did not complete the first 5 cycles of treatment and did not show improvement prior to EOT will be counted as not having improved.

6.3.2.7. Continuous endpoints

Random coefficient models will be carried out for the FKSI-19, FKSI-DRS EQ-5D-5L, and EQ-5D-5LVAS using PROC MIXED.

Outcomes are PRO post-baseline scores and the predictors are the corresponding baseline PRO score, treatment, time (treated as a continuous variable), and treatment-by-time interaction. Intercept and time are considered as random effects particular to each subject.

All available data for each patient will be used in analyses. All parameter estimates will be obtained using restricted maximum likelihood. The unstructured covariance structure will be used to define covariance between random effects (using option "Type=UN" as a part of the RANDOM statement in PROC MIXED). For the degrees-of-freedom calculations the

Kenward and Roger algorithm will be used (using option “ddfm = kr” as a part of the MODEL statement in PROC MIXED).

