2.2. Study Design

This is a Phase 3, multinational, multicenter, randomized (1:1), open-label, parallel 2-arm study in which approximately 830 patients, including a minimum of 580 PD-L1 positive patients, are planned to be randomized to receive either avelumab in combination with axitinib or sunitinib monotherapy.

- Arm A: avelumab plus axitinib;
- Arm B: sunitinib.

Patients will be stratified according to ECOG PS (0 vs 1) and region (United States vs Canada/Western Europe vs the rest of the world).

Crossover between treatment arms will not be permitted.

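### The longitudinal PRO models and the Cycle 5 improvement test leave out the randomization strata without a stated reason; adding them costs almost nothing and may gain a little precision

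*SAP*

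**What the plan says.** SAP 2.2 sets the randomization: "Patients will be stratified according to ECOG PS (0 vs 1) and region", the latter in three levels, for "approximately 830 patients, including a minimum of 580 PD-L1 positive patients". SAP 6.3.2 fixes the PRO populations: "All PRO analyses will be performed for PD-L1 positive patients and for patients unselected for PD-L1 expression and will be based on the FAS".

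Three kinds of PRO analysis follow.

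- Time to deterioration (TTD) and time to improvement (TTI) in FKSI-DRS, SAP 6.3.2.5: a Cox "Proportional Hazard model stratified by the randomization strata to calculate the hazard ratio for the experimental arm vs control arm". SAP 6.3.2.1 names TTD as the primary PRO endpoint, and protocol 9.3.2 also asks for a stratified log-rank test.
- Improvement at Cycle 5, SAP 6.3.2.6: "Chi-square test will be used to compare the proportions between the experimental arm and control arm". No stratum or covariate is named.
- Scores over time (FKSI-19, FKSI-DRS, EQ-5D index and VAS), SAP 6.3.2.7: "Outcomes are PRO post-baseline scores and the predictors are the corresponding baseline PRO score, treatment, time (treated as a continuous variable), and treatment-by-time interaction". For the random part, "Intercept and time are considered as random effects particular to each subject".

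No other section adds ECOG PS or region to the last two analyses.

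**The concern.** FKSI-DRS is analysed with the strata when the outcome is time to a 3-point change, and without them when the outcome is the score itself or improvement at Cycle 5. Among binary outcomes, tumor response gets a CMH test over the strata, while PRO improvement gets an unstratified test.

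Stratified randomization balances the arms on ECOG PS and region. An analysis that ignores these factors leaves their between-patient variance in the error term and makes no use of the balance. Some link with outcome is plausible: ECOG PS rates restriction of activity, FKSI-DRS asks about energy and fatigue, and EQ-5D asks about mobility and usual activities. PRO is a listed secondary endpoint with its own objective (protocol 2.1 and 2.2), so avoidable imprecision deserves a look.

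**Working it through.** The documents give no SD, effect size, significance level or power for these two analyses, so there is no plan figure to reproduce. They also give no figure for how well the strata predict PRO outcome. Every strata effect below is an assumption, and each range starts at zero.

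**Step 1. The SAP's methods side by side.**

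| Outcome | SAP section | Method | Strata used |
|---|---|---|---|
| PFS, OS | 6.1.1.1, 6.1.2.1 | stratified log-rank and Cox | yes |
| Objective response | 6.2.2.5 | CMH | yes |
| TTD, TTI | 6.3.2.5 | stratified Cox | yes |
| Cycle 5 improvement | 6.3.2.6 | chi-square | no |
| PRO scores over time | 6.3.2.7 | random intercept and slope | no |

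The strata form 2 x 3 = 6 cells.

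**Step 2. The random-coefficient model.** Assumptions: 580 patients, 1:1; intercept SD 4, slope SD 0.25 per cycle, correlation -0.2, residual SD 2.5; 2 to 16 assessments per patient; ECOG 1 in 40%; regions 30/30/40%. The strata shift the patient's level, given baseline score, by b points for ECOG 1 and by r points per region step.

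Strata variance = 0.24 b² + 0.69 r², where 0.24 = 0.4 x 0.6 and 0.69 is the variance of region scored 0, 1, 2. Share of intercept variance = strata variance / (strata variance + 16).

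- b = 1, r = 0.5: 0.24 + 0.1725 = 0.4125; 0.4125/16.4125 = 2.5%
- b = 2, r = 0.5: 0.96 + 0.1725 = 1.1325; 1.1325/17.1325 = 6.6%
- b = 3, r = 1: 2.16 + 0.69 = 2.85; 2.85/18.85 = 15.1%

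Standard errors come from generalized least squares, Cov = (Σ X'V⁻¹X)⁻¹ with V = ZGZ' + σ²I. Without adjustment, the strata variance is added to the intercept variance in G. The arm difference at Cycle 5 is the treatment coefficient plus 5 times the treatment-by-time coefficient. The ratios are adjusted over unadjusted SE.

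| Strata share of intercept variance | Arm difference at Cycle 5 | Treatment-by-time |
|---|---|---|
| 0% | 1.003 | 1.000 |
| 2.5% | 0.991 | 1.000 |
| 6.6% | 0.971 | 1.000 |
| 15.1% | 0.927 | 0.999 |

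The gain runs from nothing to about 7%, and only for the arm difference at a fixed time. Strata main effects remove variance between patients' levels, whereas the slope contrast rests on change within patients.

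**Step 3. The Cycle 5 test.** 6,000 simulated trials per setting; allocation balanced within the six cells; logistic outcome with intercept -1.2; two-sided 5% level. Treatment log odds ratio 0.5 (OR 1.65) at N = 580 and 0.42 (OR 1.52) at N = 830. Strata shares as in step 2.

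| Log odds: ECOG; region step | N = 580, chi-square / CMH power | N = 830, chi-square / CMH power |
|---|---|---|
| 0; 0 | 77.4 / 77.3% | 76.9 / 76.9% |
| 0.4; 0.2 | 76.8 / 77.0% | 76.0 / 76.5% |
| 0.8; 0.3 | 73.5 / 75.1% | 74.5 / 75.7% |
| 1.2; 0.5 | 72.0 / 75.1% | 69.9 / 73.5% |

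The gain runs from zero to 3.1 points at 580 and 3.6 points at 830. The Monte Carlo standard error of a single power figure is about √(0.75 x 0.25/6000) = 0.6 points, so the first two rows show no clear difference.

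Under the null with the strongest strata effects, the chi-square test rejects in 4.3% (N = 580) and 4.0% (N = 830) of trials, against 5.3% and 5.0% for CMH. The chi-square error is on the conservative side.

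**The case against.** The strongest reply is that the loss may be nil. The 6.3.2.7 model already contains the baseline score, which probably absorbs part of any ECOG effect, and the Cycle 5 outcome is itself a change from baseline. That ECOG PS predicts the level of a symptom score does not show that it predicts later change. This stands, and it is why the consequence is conditional.

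It is also fair that nothing decisive depends on these analyses. The alpha-controlled hypotheses H01 to H04 concern PFS and OS only, and TTD is stratified already. This stands too, and limits the weight of the point. It does not explain the omission. SAP 3.4.2 declines covariate adjustment only for baseline characteristics other than the strata.

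A reader might infer more than the documents support:

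- *That the standard errors are certainly too large.* This needs the strata to be prognostic given baseline, which the documents do not show.
- *That the loss equals many patients.* The single-outcome formula √(1 - R²) with R² = 10% gives an SE ratio of 0.949, or 1/0.90, about 11% more patients. That formula does not describe a random intercept and slope model, in which the treatment-by-time term gains essentially nothing.
- *That the SAP contradicts itself.* SAP 3.4.2 commits to stratification only for PFS and OS; the protocol asks for a repeated measures model for EQ-5D without listing covariates; and the subgroup tests in SAP 6.4 are unstratified by design. The handling is uneven and unexplained, but no section conflicts with another.
- *That the Cycle 5 confidence interval is too wide.* SAP 6.3.2.6 plans a test and no between-arm interval.

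**Conclusion.** The omission is certain; its cost is small and conditional. If the strata predict outcome beyond baseline PRO, the planned analyses lose up to about 7% of the standard error of the arm difference at a fixed time and up to about 4 power points at Cycle 5. The upper ends need strong strata effects: 15% of the between-patient intercept variance, or log odds of 1.2 for ECOG PS and 0.5 per region step. With no such effect the loss is zero.

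The Cycle 5 test is the clearer case, because no baseline covariate enters it. The simulation assumed balance within all six cells. In the PD-L1 positive set that balance is only approximate, since PD-L1 status is not a stratification factor, so the conservatism of the chi-square test may be milder there.

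In randomized arms the omission by itself causes neither bias nor type I error inflation. TTD, the confirmatory PFS and OS tests, and the trial's conclusions on them are untouched. This is a modest improvement, not a defect that threatens a result.

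**What to change.** In SAP 6.3.2.7, add ECOG PS and region, as recorded in the IRT system, as fixed effects in each model.

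In SAP 6.3.2.6, replace the chi-square test with a CMH test stratified by the same factors, and report the stratified odds ratio or risk difference with its 95% CI. Choose the measure in advance: a stratified odds ratio is conditional on the strata and is not the same quantity as the crude one. The response analysis in 6.2.2.5 already uses this method, so its specification can be reused.

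The cost is about two SAP sentences and three model degrees of freedom (one for ECOG PS, two for region). The strata are already in the data. If they turn out to carry no information, the standard error of the arm difference rises by about 0.3% at 580 patients. With the assumed mix the smallest cell would hold about 580 x 0.4 x 0.3 = 70 patients, so the six cells are supportable. No additional data collection is needed.
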